## Stratification factors:

Some of the key prognostic factors for HCC include Eastern Cooperative Oncology Group (ECOG) performance status, macrovascular invasion, geographic region, etiology of liver disease, extra-hepatic disease, Child-Pugh status, and baseline AFP (Llovet et al 2008a, Bruix et al 2012, Cheng et al 2012). The 3 important factors selected for stratification were macrovascular invasion (yes versus no), etiology of liver disease (Confirmed HBV versus confirmed HCV versus others), and ECOG performance status (0 versus 1). Three factors, resulting in 12 different combinations, ensure sufficient events in each of the combinations to allow for precise estimation of treatment effects and adequate power for analysis.

Geographical region was not selected because etiology of liver disease accounts for some of the different prognosis observed in the different geographic regions. Similarly, macrovascular invasion and extra-hepatic disease both represent the impact of tumor burden. The selection of patients with Child-Pugh class A removed the need to include Child-Pugh status. Hence, the proposed stratification factors are considered appropriate for the proposed Phase III study.

Subjects will be stratified to the HBV positive cohort if subjects:

- Test positive for HBV (test positive for hepatitis B surface antigen (HBsAg) and/or hepatitis B core antibodies (anti-HBcAb) with detectable HBV DNA ( $\geq 10$  IU/ml or above the limit of detection per local or central lab) ([Appendix I](#))). Subjects must be treated with antiviral therapy, as per institutional practice, to ensure adequate viral suppression ( **$HBV\ DNA \leq 2000\ IU/mL$** ) prior to enrolment.

Subjects will be stratified to the HCV positive cohort if subjects

- Subjects will be stratified to the HCV positive cohort if they test positive for HCV or have a history of HCV infection (Refer to Appendix I).

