#### **3.1 Inclusion criteria**

For inclusion in the study, patients should fulfill the following criteria:

1. Age  $\geq$ 18 years at the time of screening
2. Body weight  $>$ 30 kg.
3. Written informed consent and any locally required authorization (eg, Health Insurance Portability and Accountability Act in the US, European Union [EU] Data Privacy Directive in the EU) obtained from the patient/legal representative prior to performing any protocol-related procedures, including screening evaluations.
4. Confirmed HCC based on histopathological findings from tumor tissues.
5. Must not have received prior systemic therapy for HCC.
6. Must not be eligible for locoregional therapy for unresectable HCC. For patients who progressed after locoregional therapy for HCC, locoregional therapy must have been completed  $\geq$ 28 days prior to the baseline scan for the current study.
7. Barcelona Clinic Liver Cancer (BCLC) stage B (that is not eligible for locoregional therapy) or stage C. (refer to appendix J)
8. Child-Pugh Score class A. (refer to table 9)
9. ECOG performance status of 0 or 1 at enrollment. (refer to section 5.2.6)
10. Patients with HBV infection, characterized by positive hepatitis B surface antigen (HBsAg) and/or hepatitis B core antibodies (anti-HBcAb) with detectable HBV DNA ( $\geq$ 10 IU/ml or above the limit of detection per local or central lab standard), must be treated with antiviral therapy, as per institutional practice, to ensure adequate viral suppression (HBV DNA  $\leq$ 2000 IU/mL) prior to enrollment. Patients

must remain on antiviral therapy for the study duration and for 6 months after the last dose of study medication. Patients who test positive for anti-hepatitis B core (HBc) with undetectable HBV DNA (<10 IU/ml or under the limit of detection per local or central lab standard) do not require anti-viral therapy prior to enrollment. These subjects will be tested at every cycle to monitor HBV DNA levels and initiate antiviral therapy if HBV DNA is detected ( $\geq 10$  IU/ml or above the limit of detection per local or central lab standard). HBV DNA detectable subjects must initiate and remain on antiviral therapy for the study duration and for 6 months after the last dose of study medication.

11. Patients with HCV infection must have confirmed diagnosis of HCV characterized by the presence of detectable HCV RNA or anti-HCV antibody upon enrollment (management of this disease is per local institutional practice).

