13. Patients with main portal vein thrombosis (i.e. thrombosis in the main trunk of the portal vein, with or without blood flow) on baseline imaging.
14. Active or prior documented GI bleeding (eg, esophageal varices or ulcer bleeding) within 12 months.  
(Note: For patients with a history of GI bleeding for more than 12 months or assessed as high risk for esophageal variceal by the Investigator, adequate endoscopic therapy according to institutional standards is required.)
15. Patient currently exhibits symptomatic or uncontrolled hypertension defined as diastolic blood pressure  $>90$  mmHg or systolic blood pressure  $>140$  mmHg.
16. Any condition interfering with swallowing pills, uncontrolled diarrhea, or other contraindication to oral therapy.
17. Active or prior documented autoimmune or inflammatory disorders (including inflammatory bowel disease [eg, colitis or Crohn's disease], diverticulitis [with the exception of diverticulosis], systemic lupus erythematosus, Sarcoidosis syndrome, or Wegener syndrome [granulomatosis with polyangiitis, Graves' disease, rheumatoid arthritis, hypophysitis, uveitis, etc]). Patients without active disease in the last 5 years are excluded unless discussed with the Study Physician and considered appropriate for study participation.

The following are exceptions to this criterion:

- Patients with vitiligo or alopecia
- Patients with hypothyroidism (eg, following Hashimoto syndrome) stable on hormone replacement
- Any chronic skin condition that does not require systemic therapy
- Patients with celiac disease controlled by diet alone

18. Patients co-infected with HBV and HCV, or co-infected with HBV and hepatitis D virus (HDV). HBV positive (presence of HBsAg and/or anti-HBcAb with detectable HBV DNA); HCV positive (presence of anti-HCV antibodies); HDV positive (presence of anti-HDV antibodies).
19. Uncontrolled intercurrent illness, including but not limited to, ongoing or active infection, symptomatic congestive heart failure, uncontrolled hypertension, unstable

angina pectoris, cardiac arrhythmia, ILD, serious chronic GI conditions associated with diarrhea, inferior vena cava thrombosis, or psychiatric illness/social situations that would limit compliance with study requirement, substantially increase the risk of incurring AEs, or compromise the ability of the patient to give written informed consent.

20. History of another primary malignancy except for:

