f Free T3 or free T4 will only be measured if TSH is abnormal or if there is clinical suspicion of an AE related to the endocrine system.

g If thyroid function, AFP and virology assessment are performed within 14 days prior to Day 1 (first infusion day), they do not need to be repeated at Day 1. These assessments may be performed more frequently, if clinically indicated.

h Patients who are anti-HBc positive and HBV DNA undetectable (<10UL/ml or under the limit of detection per local or central lab standard) at screening are considered as HBV negative. If these patients are stratified to HCV positive or others, they still must be tested for HBV DNA viral load every cycle. In case of HBV reactivation (HBV DNA  $\geq$ 10 IU/ml or above the limit of detection per local or central lab standard), patients must be treated with antiviral therapy, as per institutional

practice, to ensure adequate viral suppression (HBV **CCI**) prior to enrollment. Patients must remain on antiviral therapy for the study duration and for 6 months after the last dose of study medication.

i HCV **CCI** will be assessed during treatment only if HCV RNA is positive at baseline or Day 1.

j HCV **CCI** will only be collected at baseline or Day 1 **CCI**

k For women of childbearing potential only. A urine or serum pregnancy test is acceptable. Women of childbearing potential are required to have a pregnancy test within 7 days prior to the first dose of study drug(s) and then every 4 weeks. Pregnancy test may be performed within 3 days prior to Day 1, but results must be available and reviewed by the treating physician or Investigator prior to commencing an infusion.

l Durvalumab PK pre-dose samples should be collected within 1 hour before the beginning of durvalumab infusion. Durvalumab and tremelimumab PK pre-dose samples should be collected within 1 hour before the beginning of both durvalumab and tremelimumab infusions (when applicable).

m Durvalumab post-dose samples should be collected within 10 minutes after the end of durvalumab infusion. Tremelimumab post-dose samples should be collected within 10 minutes after the end of tremelimumab infusion.

n For AEs/SAEs reported during screening, additional information such as medical history and concomitant medications may be needed. Any AEs/SAEs detected on non-study-related visits should be reported.

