**Table 3 Schedule of assessments for sorafenib**

a Cycles are 28 days long such that patients receive uninterrupted sorafenib 400 mg CCI treatment.

**b** Visits continue every 4 weeks.

c Informed consent of study procedures and tumor biopsy sample may be obtained prior to the 28-day screening window, if necessary, in order to permit tumor biopsy sample acquisition prior to randomization. If laboratory or imaging procedures were performed for alternate reasons prior to signing consent, these can be used for screening purposes with consent of the patient. However, all screening laboratory and imaging results must have been obtained within 28 days of randomization. Note: tumor biopsy is optional for the China cohort.

- d Vital signs should be collected at each visit.
- e Any clinically significant abnormalities detected require triplicate ECG results.
- f If screening laboratory assessments are performed within 3 days prior to Day 1, they do not need to be repeated at Day 1.
- g Free T3 or free T4 will only be measured if TSH is abnormal or if there is clinical suspicion of an AE related to the endocrine system.
- h Patients who are anti-HBc positive and HBV **CCI** undetectable (<10UL/ml or under the limit of detection per local or central lab standard) at screening are considered as HBV negative. If these patients are stratified to HCV positive or others, they still must be tested for HBV **CCI** viral load every cycle. In case of HBV reactivation (HBV **CCI** ≥10 IU/ml or above the limit of detection per local or central lab standard), patients must be treated with antiviral therapy, as per institutional practice, to ensure adequate viral suppression (HBV **CCI** ≤2000 IU/mL) prior to enrollment. Patients must remain on antiviral therapy for the study duration and for 6 months after the last dose of study medication.
- i HCV **CCI** will be assessed during treatment only if HCV **CCI** is positive at baseline or Day 1.
- j HCV **CCI** will only be collected at baseline or Day 1 **CCI**.
- k For women of childbearing potential only. A urine or serum pregnancy test is acceptable. Women of childbearing potential are required to have a pregnancy test within 7 days prior to the first dose of study drug(s) and then every 4 weeks. Pregnancy test may be performed within 3 days prior to Day 1, but results must be available and reviewed by the treating physician or Investigator prior to receiving drug.

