## **Appendix I Hepatitis stratification**

Patients will be stratified to the HBV positive cohort if they test positive for HBsAg or have occult HBV infection (positive anti-HBc with detectable HBV DNA) (Table 21).

Patients Subjects will be stratified to the HCV positive cohort if they test positive for HCV or have a history of HCV infection

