**Table 21 Hepatitis B Stratification Guidance**

Test	Result	Interpretation	Action	Stratified to Hepatitis B
HBsAg	Negative	Susceptible	None	No
anti-HBc	Negative			
anti-HBs	Negative			
HBsAg	Negative	Immune due to natural infection or chronic infection without antigenemia	Test HBV CCI load: 
 
• If <10 IU/ml, no antiviral treatment required. Continue testing monthly to ensure levels do not exceed 10 IU/ml.
 
• If ≥10 IU/ml, start anti-viral treatment and maintain treatment until 6 months post last dose study drug.
 
	If HBV CCI load ≥10 IU/ml: Yes
anti-HBc	Positive			
anti-HBs	Positive			HBV CCI load <10 IU/ml: No
HBsAg	Negative	Immune due to hepatitis B vaccination	None	No
anti-HBc	Negative			
anti-HBs	Positive			
HBsAg	Positive	Acute Infection	Start anti-viral treatment and maintain treatment until 6 months post last dose study drug	Yes
anti-HBc	Positive			
IgM anti-HBc	Positive			
anti-HBs	Negative			
HBsAg	Positive	Chronic infection	Start anti-viral therapy and maintain treatment until 6 months post last dose study drug	Yes
anti-HBc	Positive			
IgM anti-HBc	Negative			
anti-HBs	Negative			
HBsAg	Negative	4 potential interpretations:	Test HBV CCI load:	If HBV CCI load ≥10 IU/ml: Yes
anti-HBc	Positive	
 
• Resolved infection (most common)
 
	
 
• If <10 IU/ml, no treatment required. Continue testing monthly to ensure levels do not exceed 10IU/ml.
 
	
anti-HBs	Negative	
 
• False-positive anti-HBc: susceptible
 
• Low-level chronic infection
 
• Resolving acute infection
 
	
 
• If ≥10 IU/ml, start anti-viral treatment and maintain treatment until 6 months post last dose study drug
 
	If HBV CCI load <10 IU/ml: No

Note: If the limit of detection in local and central lab is higher than 10 IU/ml, sites should follow the local lab standard.

CCI ; IgM Immunoglobulin M; HBc Hepatitis B core; HBs Hepatitis B surface; HBsAg Hepatitis B surface antigen; HBV Hepatitis B virus.

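### Footnote h of Tables 2 and 3 calls virally suppressed HBsAg-positive patients HBV negative, against Appendix I and Table 21

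*Protocol*

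**What the plan says.** Footnote h in the Table 2 schedule of assessments covers "Patients who are anti-HBc positive and HBV DNA undetectable" and says that they "at screening are considered as HBV negative. If these patients are stratified to HCV positive or others, they still must be tested" for HBV DNA at every cycle. Footnote h of Table 3, for the sorafenib arm, carries the same rule: "at screening are considered as HBV negative. If these patients are stratified to HCV positive or others". Neither footnote mentions HBsAg.

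Appendix I gives the stratification rule: "Patients will be stratified to the HBV positive cohort if they test positive for HBsAg or have occult HBV infection". Detectable DNA is required only for the occult form. Table 21 works this out row by row. Its chronic-infection row (HBsAg positive, anti-HBc positive) assigns the patient to the hepatitis B stratum and instructs: "Start anti-viral therapy and maintain treatment until 6 months post last dose study drug". No DNA level enters that row.

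Three other places bear on HBV status. Section 1.2, under the stratification factors, refers to Appendix I and reads "Test positive for HBV (test positive for hepatitis B surface antigen (HBsAg) and/or hepatitis B core antibodies (anti-HBcAb) with detectable HBV DNA". Inclusion criterion 10 opens with "Patients with HBV infection, characterized by positive hepatitis B surface antigen (HBsAg) and/or hepatitis B core antibodies (anti-HBcAb) with detectable HBV DNA". Exclusion criterion 18 defines "HBV positive (presence of HBsAg and/or anti-HBcAb with detectable HBV DNA".

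**The concern.** Footnote h states a classification rule with one condition missing. Read literally, it applies to an HBsAg-positive patient whose DNA is suppressed by antivirals and calls that patient HBV negative. Section 3.3 describes the third etiology stratum as negative for both HBV and HCV, so a site following the footnote could enter a chronic HBV carrier there.

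Three uses of the label could be affected:

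- the etiology stratum entered in the IWRS;
- the etiology subgroups in Sections 8.5.6.1 and 8.5.6.2;
- the duty to continue antivirals, which the note in Section 5.2.1 attaches to patients who are HBV positive.

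**Working it through.** No sample size, alpha or event count is involved, so the check compares the texts.

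**Is the patient realistic?** Inclusion criterion 10 requires HBV-infected patients to be on antiviral therapy with HBV DNA at or below 2000 IU/mL before enrollment. That range includes values below 10 IU/ml, which footnote h calls undetectable (or below the laboratory's own limit). An HBsAg-positive patient with undetectable DNA can therefore enter the trial.

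**What does each text do with an anti-HBc-positive patient?**

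| Screening result (all anti-HBc positive) | Footnote h | Appendix I and Table 21 | Conflict |
|---|---|---|---|
| HBsAg negative, DNA below 10 IU/ml | HBV negative | Not HBV stratum | No |
| HBsAg negative, DNA 10 IU/ml or more | Does not apply | HBV stratum | No |
| HBsAg positive, DNA 10 IU/ml or more | Does not apply | HBV stratum | No |
| HBsAg positive, DNA below 10 IU/ml | HBV negative | HBV stratum, antivirals required | **Yes** |

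The conflict is confined to the last line. Adding HBsAg-negative to the footnote removes it and changes no other line.

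**Table 21 by row.** It has 6 serology patterns, of which 4 are anti-HBc positive. In 2 of those 4, both HBsAg negative, the 10 IU/ml threshold decides the stratum, and footnote h agrees. In the other 2, acute and chronic infection, both HBsAg positive, the answer is yes with no DNA condition. Footnote h contradicts these 2 when DNA is undetectable.

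**Which text is out of line?** Seven places state HBV status:

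- Appendix I and Table 21 (2) explicitly class an HBsAg-positive patient as HBV regardless of DNA.
- Section 1.2, the first sentence of inclusion criterion 10 and exclusion criterion 18 (3) do so on their natural reading. The grammar would also allow the DNA condition to attach to HBsAg.
- Footnote h in Tables 2 and 3 (2) leaves HBsAg out.

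That is 2 + 3 = 5 of 7 on one side, with only 2 of the 5 explicit. These are counts of text, not of patients. Appendix I and Table 21 settle the matter, because they are the stratification guidance and Section 1.2 refers to Appendix I.

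**What is not affected?** The row of Table 2 for patients without HBV or HCV still requires DNA testing when anti-HBc is positive and DNA undetectable, so monitoring continues even for a mislabelled patient. The etiology label is fixed before randomization, so a wrong one does not invalidate the stratified log-rank comparison.

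**The case against.** The strongest reply is that the governing rule is stated and easy to find. Section 1.2 sends the reader to Appendix I, and Table 21 has a column for the stratum. Footnote h sits on a virology row of a visit schedule, and its instruction concerns monitoring. Its second sentence is conditional on a stratum decided elsewhere, and it names HCV positive or others without assigning either. It was very probably written with HBsAg-negative patients in mind. The antiviral duty is also covered by the first sentence of inclusion criterion 10 and by Table 21. The row count overstates the practical conflict, since acute infection with undetectable DNA is unlikely. Finally, the choice between IWRS and derived etiology for subgroups is commonly left to the SAP.

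Most of this stands, and it keeps the point small. It does not remove the contradiction. In Table 2 the footnote is attached to the virology assessment of all screened patients, which includes HBsAg, so nothing in its placement limits it to HBsAg-negative patients. No text says which source prevails over the footnote. The probable intent is a reason the correction is safe. Deriving the subgroup variable is a recommendation that follows from the contradiction; its absence from the protocol is not itself an error.

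**Conclusion.** Footnote h is wrong as written in both tables. It gives the opposite HBV status from Appendix I and Table 21 for one realistic type of patient: HBsAg positive, anti-HBc positive, DNA undetectable.

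The severity is minor. The consequences are possible misclassification between the HBV stratum and the others stratum, the same misclassification in subgroup analyses that Section 8.5.6.1 describes as supportive, and some loss of clarity about continued antivirals. How many patients are concerned is unknown, because the protocol gives neither the etiology split nor the share of HBsAg-positive patients with undetectable DNA. Nothing in it shows that any patient was in fact misclassified.

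Timing limits what can still be repaired. Version 8.0 is dated June 2024, and Section 9.3 places the final primary analysis in Q4 2021, so rewording cannot alter strata already assigned. For those patients only the subgroup classification can be corrected. The eligibility wording can still matter for treatment through progression and rechallenge, because Section 7.2.1.3 reapplies all eligibility criteria except inclusion 5 and 12 and exclusion 23.

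**What to change.** Insert HBsAg-negative before the anti-HBc condition in footnote h of Table 2 and of Table 3. Make the same insertion in the sentence of inclusion criterion 10 that exempts anti-HBc-positive patients with undetectable DNA from antivirals. That last change is for consistency only, since the criterion's first sentence already covers HBsAg-positive patients.

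For the etiology subgroup analyses, classify HBV status by Appendix I and Table 21 from the screening HBsAg, anti-HBc and HBV DNA results. The stratified log-rank test needs no change.

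The cost is one inserted term in three places and one derived variable. The serology is already scheduled for every screened patient, so no further tests or patients are needed.

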**Table 3 Schedule of assessments for sorafenib**

a Cycles are 28 days long such that patients receive uninterrupted sorafenib 400 mg CCI treatment.

**b** Visits continue every 4 weeks.

c Informed consent of study procedures and tumor biopsy sample may be obtained prior to the 28-day screening window, if necessary, in order to permit tumor biopsy sample acquisition prior to randomization. If laboratory or imaging procedures were performed for alternate reasons prior to signing consent, these can be used for screening purposes with consent of the patient. However, all screening laboratory and imaging results must have been obtained within 28 days of randomization. Note: tumor biopsy is optional for the China cohort.

- d Vital signs should be collected at each visit.
- e Any clinically significant abnormalities detected require triplicate ECG results.
- f If screening laboratory assessments are performed within 3 days prior to Day 1, they do not need to be repeated at Day 1.
- g Free T3 or free T4 will only be measured if TSH is abnormal or if there is clinical suspicion of an AE related to the endocrine system.
- h Patients who are anti-HBc positive and HBV **CCI** undetectable (<10UL/ml or under the limit of detection per local or central lab standard) at screening are considered as HBV negative. If these patients are stratified to HCV positive or others, they still must be tested for HBV **CCI** viral load every cycle. In case of HBV reactivation (HBV **CCI** ≥10 IU/ml or above the limit of detection per local or central lab standard), patients must be treated with antiviral therapy, as per institutional practice, to ensure adequate viral suppression (HBV **CCI** ≤2000 IU/mL) prior to enrollment. Patients must remain on antiviral therapy for the study duration and for 6 months after the last dose of study medication.
- i HCV **CCI** will be assessed during treatment only if HCV **CCI** is positive at baseline or Day 1.
- j HCV **CCI** will only be collected at baseline or Day 1 **CCI**.
- k For women of childbearing potential only. A urine or serum pregnancy test is acceptable. Women of childbearing potential are required to have a pregnancy test within 7 days prior to the first dose of study drug(s) and then every 4 weeks. Pregnancy test may be performed within 3 days prior to Day 1, but results must be available and reviewed by the treating physician or Investigator prior to receiving drug.
- l For AEs/SAEs reported during screening, additional information such as medical history and concomitant medications may be needed. Any AEs/SAEs detected on non-study-related visits should be reported.
- m In the event patient discontinued treatment after first PD, first PD should be used as disease progression to trigger a patient for follow-up ePRO assessments.
- n For patients who are treated through disease progression, the schedule of assessments should be followed as per the initial treatment period.
- o **CCI** will only be administered in those countries where a linguistically validated version is available.
- p Optional tumor collection upon confirmed PD.
- q RECIST 1.1 assessments will be performed on images from CT (preferred) or MRI, each preferably with IV contrast of the chest, abdomen (including liver and adrenal glands), and pelvis. Pelvic imaging is recommended only when primary or metastatic disease in the pelvic region is likely. Additional anatomy should be imaged based on signs and symptoms of individual patients at baseline and follow-up. Baseline assessments should be performed no more than 28 days before the date of randomization and, ideally, should be performed as close as possible to and prior to the start of study drug(s). Tumor assessments should continue on schedule until RECIST 1.1-defined radiological progression followed by a subsequent scan if clinically feasible, evaluated by Confirmation of Radiological Progression criteria ([Appendix B](#)). The subsequent scans should be performed preferably at the next scheduled imaging visit and no less than 4 weeks after the prior assessment of PD (in the absence of clinically significant deterioration). If an unscheduled assessment was performed and the patient has not progressed, every attempt should be made to perform the subsequent assessments at their next scheduled visit.
- r If thyroid function, AFP and virology assessment are performed within 14 days prior to Day 1 (first infusion day), they do not need to be repeated at Day 1. These assessments may be performed more frequently, if clinically indicated.
- s Samples for patients enrolled in China will be collected according to local laws and regulations

Note: All assessments on treatment days are to be performed prior to administration, unless otherwise indicated.

AE Adverse event; AFP Alpha-fetoprotein;; aPTT Activated partial thromboplastin time; **CCI** ; C Cycle; CT Computed tomography; **CCI** ; **CCI** ECG Electrocardiogram; ECOG Eastern Cooperative Oncology Group; EORTC European Organisation for Research and Treatment of Cancer; ePRO Electronic Patient-reported Outcome; **CCI** HBc Hepatitis B core; HBe Hepatitis B e; HBeAG Hepatitis B e antigen; HBs Hepatitis B surface; HBsAg Hepatitis B surface antigen; HBV Hepatitis B virus; HCV Hepatitis C virus; HDV Hepatitis D virus; HIV Human immunodeficiency virus; **CCI** ; INR International normalized ratio; IV intravenous; **CCI** ; **CCI** ; MRI Magnetic resonance imaging; NA Not applicable; PD Progression of disease; PD-L1 Programmed cell death ligand 1; PGIC Patients' Global Impression of Change; PRO Patient-reported outcome; **CCI**

PT Prothrombin time; **CCI** [REDACTED]; Q8W Every 8 weeks; Q12W Every 12 weeks; **CCI** [REDACTED]; RECIST 1.1 Response evaluation criteria in solid tumors version 1.1; SAE Serious adverse event; **CCI** [REDACTED]; T3 Triiodothyronine; T4 Thyroxine; TSH Thyroid-stimulating hormone.

